## 10.2 MEASURES TO MINIMIZE BIAS

## 10.2.1 ENROLLMENT/ RANDOMIZATION/ MASKING PROCEDURES

#### Recruitment Methods and Consenting Process:

At the baseline visit, the participants will be consented to participate in the study. After participating in the boxing match, the enrolled boxers will be re-screened and if the boxer has a Rivermead symptom score > 1 on at least 3 items from the Rivermead Post-Concussion Questionnaire or has greater than 25 blows to the head, the participant will be informed of their eligibility to participate in the study and the potential risks associated with this clinical trial.

A copy of the signed consent form will be provided to the participant/family, and one copy will remain in a locked storage facility. Both women and minorities will be enrolled in this study. Due to the study population, children will not be enrolled in this study. Previously, we have enrolled 125 boxers from the North Texas area to participate in both observational and interventional clinical trials. Recently we completed a Department of Defense (DOD) observational study aimed at measuring early brain biomarkers of injury in professional boxers. We identified numerous early predictors of outcome in these athletes. Our dropout rate is very low and previously the boxers were compliant with the study procedures (self-administering study medication, neuropsychological testing, MRI procedures). We expect a dropout rate of 10-20% and will enroll a total of 110-120 boxers to complete the proposed studies.

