The participants in **group 1** (single therapy) will consist of the active boxers/MMA fighters that experience significant sub-concussive blows or a concussion during competition. In this group, 65, professional male/female boxers/MMA fighters within the North Texas region will be screened and about 50 concussed athletes will be enrolled. The athletes that have at least 25 blows to the head and a Symptom Score > 1 on at least 3 items from the Rivermead Post-Concussion Questionnaire following their fight will be enrolled in this study. The research subjects will be treated with sildenafil (60mg), once at 2 hours after experiencing a concussion.

**Group 2** will consist of the active boxers/MMA fighters that experience significant subconcussive blows or a concussion during competition. In this group, 65, professional male/female boxers/MMA fighters within the North Texas region will be screened and about 50 concussed athletes will be enrolled. The athletes that have at least 25 blows to the head and a Symptom Score > 1 on at least 3 items from the Rivermead Post-Concussion Questionnaire following their fight will be enrolled in this study. Once enrolled, the subjects will be treated with sildenafil (60mg) once-a-day for 14 days.

**Healthy Control group:** In this study, 80, age (between 18 and 35)-matched healthy controls will be enrolled. The control subjects will participate in neuropsychological testing, blood/saliva collection, and the MR imaging procedures. Healthy controls will be tested in group 1 (n=40) and 2 (n=40) and randomized to receive either sildenafil or placebo in this group.

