# 6.1.5 DOSING AND ADMINISTRATION

STU032018-063, [name], FormA-ResearchProtocol, Mod\_6, 11-25-19 (1) NIH-FDA Clinical Trial Protocol

In the first and second group, the participants will be administered either a single-dose or 14 pills of placebo or sildenafil (60mg) after suffering a concussion. The first dose will be taken at 2hours after injury.

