## 7.3 STUDY SCHEDULE

## 7.3.1 SCREENING

Boxers that meet the baseline study criteria will be approached and if interested they will be consented to participate in the study procedures. Medical and concussion history will be reviewed at the baseline time-point to determine which boxers will be considered to participate in the study. The research coordinator/boxing consultant will identify the athletes that have experienced greater than 25 blows to the head or a Symptom Score > 1 on at least 3 items from the Rivermead Post-Concussion Questionnaire following the boxing match. Once the subject has been identified, the research personnel will review the subject's chart to determine if they meet criteria for enrollment into the study. If so, the participant will be approached to obtain consent where the patient has the right to ask questions about the study.

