## 10 STATISTICAL CONSIDERATIONS

#### 10.1 STATISTICAL AND ANALYTICAL PLANS

#### STATISTICAL ANALYSIS PLAN

#### Study design and randomization scheme

Once eligibility is confirmed, based upon defined inclusion and exclusion criteria, randomization will occur within 2 hours of a bout. The placebo-controlled double-blind design will diminish concern about predictability of treatment assignments. The unblinded study biostatistician will prepare a randomization schedule. Randomization will be 1:1 sildenafil:placebo, and will be in blocks of 2. Treatment allocation will be determined via a computer program that automatically generates random digits. Investigators associated with this study will not have access to the randomization schedule. The randomization program will also record the assignments to the corresponding boxers in the database and will display the assignments on the screen for action by the study coordinators.

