#### Outcomes

**Primary endpoints-** The absolute changes in global and regional CBF/CVR to hypercapnia and improved symptoms and cognitive performance.

Secondary endpoints- Effect of sildenafil on brain biomarkers in blood after injury.

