Also, we will assess the treatment effect of sildenafil on post-concussive symptoms and cognitive performance using two-sample t-test similarly as in the primary aim, but with the secondary endpoints of symptoms. On day 1 and 30 after injury we will then calculate the difference in CBF/CVR and each of the post-concussive symptom assessments and cognitive assessments after the single treatment of sildenafil. Also, we will assess the post-concussion correlations of CBF/CVR and cognitive performance by calculating the cross-sectional Pearson correlations of CBF/CVR with symptom inventory and neuropsychological CDEs collected at Day 1 and 30 after TBI. Correlations will be calculated separately and jointly at each time point, and for each of the subdomains of neuropsychological CDEs. Multiple comparisons will be adjusted by controlling the false discovery rate (FDR).

Our secondary analyses will consist of assessing the treatment effect of sildenafil therapy on brain biomarker levels using two-sample t testing, but with the secondary endpoints of symptoms. We will then calculate the difference in brain biomarker levels at the beginning of the sildenafil therapy and after the treatment period (Day 30 vs Day 1-3). Scatter plots including both arms will be generated based on the calculated differences and two linear regression models with changes in brain biomarkers as outcomes, and changes in symptoms as independent variables will be fit to assess the association between the recovery of the TBI-related markers. Potential confounders such as gender and treatment arm indicator will be adjusted in the model.

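### The post-fight Rivermead score, on the 2-hour dosing text the only post-injury, pre-dose symptom reading, serves eligibility alone; scheduling it and adjusting for it would sharpen the athlete symptom comparison.

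*Combined protocol and SAP*

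**What the plan says.** **Endpoint.** Under Outcomes, section 10.1 gives the primary endpoints as "The absolute changes in global and regional CBF/CVR to hypercapnia and improved symptoms and cognitive performance". Later in 10.1, the Statistical analyses text calls symptoms secondary. The Rivermead is the named symptom questionnaire in sections 4.2.1 and 4.2.1.b, where it has 16 items and takes 5 minutes.

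**Post-fight reading.** Section 10.2.1 states: "After participating in the boxing match, the enrolled boxers will be re-screened". Eligibility is confirmed first, and then "randomization will occur within 2 hours of a bout". Section 6.1.5 adds: "The first dose will be taken at 2hours after injury". In that order, the re-screen score comes after injury but before allocation and dosing.

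**Schedule.** Visit 2 in section 7.3.2 lists drug administration and nothing else. Table 2 in section 7.1.1 has no post-fight column, and its symptom row starts at Day 1-3. Section 9 describes Day 1-3 as following 1 to 3 days of drug. Visit 1 includes a symptom questionnaire, but that visit precedes the fight.

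**Analysis.** Section 10.1 tests symptoms by a two-sample t-test. It takes differences on Day 1 and Day 30 in CBF/CVR and in "each of the post-concussive symptom assessments and cognitive assessments after the single treatment of sildenafil". No covariate is named. Injury severity appears among the baseline variables, but only in descriptive work and an outlier check. The one adjustment named (gender and arm) belongs to the biomarker regression.

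**Entry rule.** Section 4.1 requires "at least 25 blows to the head and a Symptom Score > 1 on at least 3 items", and section 5.1 apparently also requires symptoms. Section 7.3.1 accepts "greater than 25 blows to the head or a Symptom Score > 1 on at least 3 items", and section 10.2.1 likewise makes the two criteria alternatives.

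**The concern.** Initial severity will vary: athletes may enter after a knockout, after many blows, or with a handful of symptoms. Early symptom burden plausibly predicts later burden. The post-fight Rivermead measures that burden on the outcome's own scale before treatment can affect it, which is what a baseline covariate should do. The pre-fight questionnaire cannot stand in for it, because it precedes the injury. On the 2-hour text, the Day 1-3 score cannot either, because by then it may already reflect the drug.

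At stake is the precision of a between-arm comparison with about 25 athletes per arm in each regimen, for which the plan gives no power figure. Where the two entry criteria are alternatives, an athlete admitted on blow count may also have no post-fight score at all.

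**Working it through.** **The plan's own symptom figure.** The only power figure that involves symptoms is 82.9% for a CVR-symptom correlation of 0.4 with 50 boxers (section 10.1). By Fisher's z at two-sided 0.05, atanh(0.4) × √47 − 1.96 = 0.4236 × 6.856 − 1.96 = 0.944, which gives 82.8%. It reproduces, but it concerns a correlation and not the comparison of arms.

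**Inputs**
- About 50 athletes per regimen (section 4.1), allocated 1:1 (section 10.1): 25 per arm within a regimen, or 50 per arm if the regimens are pooled.
- r, the correlation of the post-fight score with a follow-up score, is not in the documents. I assume 0.2 to 0.7. The lower end is the plan's base-case correlation between Day 1-3 and Day 30 (section 10.1). That figure was chosen for CVR and a different pair of readings, so it is only a guide.

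**Chance imbalance.** In SD units, the standard error of the between-arm difference in mean entry score is √(2/n).
- n = 25: √0.08 = 0.28 (95% range ±1.96 × 0.283 = ±0.55)
- n = 50: √0.04 = 0.20 (±0.39)

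**Effect on the unadjusted result.** Given an imbalance δ, the expected unadjusted difference moves by r × δ. The ANCOVA residual variance is (1 − r²) times the unadjusted variance. The detectable difference at 80% power, two-sided 0.05, is (1.960 + 0.842) × √(2/n) without adjustment, that is 0.79 SD at 25 per arm and 0.56 SD at 50. With adjustment it is multiplied by √(1 − r²).

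| r (assumed) | Shift from a one-SE imbalance, 25 per arm | Cut in residual variance | Detectable difference, 25 per arm | Detectable difference, 50 per arm |
|---|---|---|---|---|
| 0.2 | 0.2 × 0.283 = 0.06 SD | 4% | 0.78 SD | 0.55 SD |
| 0.5 | 0.5 × 0.283 = 0.14 SD | 25% | 0.69 SD | 0.49 SD |
| 0.7 | 0.7 × 0.283 = 0.20 SD | 49% | 0.57 SD | 0.40 SD |

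For an assumed true difference of 0.5 SD with 50 per arm, power is 70.5% unadjusted. Adjusted, it is 72.3% (r = 0.2), 82.3% (r = 0.5) or 93.8% (r = 0.7). With 25 per arm it is 42.4% unadjusted, and 43.8%, 53.2% or 69.7% adjusted.

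**Is it the only post-injury, pre-dose reading?** Sections 6.1.5, 7.3.2 (Visit 2), 9 and 10.1 (randomization scheme) put the start of treatment about 2 hours after injury, and then it is. Three places can be read otherwise. Table 2 marks randomization and dispensing at Day 1-3. Visit 3 lists a single administration. The secondary analysis in 10.1 equates the beginning of therapy with Day 1-3. If dosing began then, the scheduled Day 1-3 Rivermead could itself precede treatment.

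**The case against.** The strongest reply is that nothing is invalid here. Allocation is random, the unadjusted t-test is unbiased, and its standard error already allows for chance imbalance in severity. An unadjusted comparison is a legitimate choice in a phase 2 study meant to inform a definitive one. All of that stands, and it limits the point to efficiency.

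The gain may also be small. At r = 0.2 it is close to nothing, and selecting athletes on this very score may narrow its range and lower r. That stands too.

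Four stronger readings are tempting, and the documents do not support them:
- **That the symptom result is biased.** Randomization rules this out. An imbalance moves one trial's estimate but does not shift its expectation.
- **That the score is thrown away.** Section 11 files symptom forms in the participant chart. The accurate statement is that the score is neither scheduled as outcome data nor named as a covariate.
- **That the score decides entry for everyone.** This fits section 4.1 and apparently 5.1. Sections 7.3.1 and 10.2.1 make it one of two routes.
- **That no other pre-dose reading could exist under any reading of the plan.** This depends on the 2-hour text, which Table 2, Visit 3 and the secondary analysis put in doubt.

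None of these answers the core omission. On either dosing reading, the post-fight score is a pre-treatment measure of severity that the analysis leaves unused.

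**Conclusion.** The point holds as a cheap gain in precision, not as a flaw in validity. The post-fight Rivermead is used for eligibility only, while the athlete symptom comparison, primary under Outcomes, is unadjusted. Whether this is the only post-injury, pre-dose reading rests on the 2-hour dosing text. The size of the gain rests wholly on r, which the documents do not give: it is negligible near 0.2 and material from about 0.5, where precision at 50 per arm matches adjusted data from 50 × 0.75 = 37.5 per arm. The point covers athletes only. The 80 controls, also randomized to drug or placebo, have no fight and so no such score.

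**What to change.** 1. Record the 16-item Rivermead total for every athlete at the post-fight re-screen, before dosing, whichever criterion qualifies them. Add a column to Table 2 and a line to Visit 2.
2. In section 10.1, compare athlete symptom scores between arms at each visit by ANCOVA adjusted for this total, in place of the unadjusted t-test. Analyse controls separately.
3. Reconcile the passages on when randomization and dosing start (6.1.5, Visit 2, section 9 and the randomization scheme against Table 2, Visit 3 and the secondary analysis). Do the same for the entry rule (4.1 and 5.1 against 7.3.1 and 10.2.1) and for whether symptoms are primary or secondary in 10.1.

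The cost is one 5-minute form for athletes who would otherwise be admitted on blows alone, one schedule column and some SAP wording. No visit or participant is added. The downside is that the gain will be small if r is near 0.2.

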## 4 STUDY DESIGN AND ENDPOINTS

#### 4.1 DESCRIPTION OF THE STUDY DESIGN

In this placebo-controlled, double-blinded clinical trial, approximately 100 boxers/MMA fighters that have experienced a concussion or a significant number of sub-concussive blows will be treated with a placebo pill or Viagra® (sildenafil; 60mg) once (single-dose therapy) or once-a-day for 14 days. This is a phase 2 study that will be conducted at a single-site (UTSWMC, Dallas, Texas).

Prior to competition, the medical/concussion history and a blood (8ml) and saliva sample will be collected at the baseline (pre-fight) visit. Also, a battery of neuropsychological exams (NIH Common Data Elements) and a magnetic resonance imaging (MRI) scan will be performed at UT Southwestern Medical Center Advanced Imaging Research Center to obtain cognitive, structural, and functional baseline data.

At day1-3 and 30 after injury, the boxers will undergo the MRI structural and MRI BOLD (with hypercapnia) procedures at UT Southwestern Medical Center Advanced Imaging Resource Center. The subjects will also undergo neurpsychological testing, and blood/saliva collection for tests to determine the efficacy of sildenafil. A randomization schedule will be prepared by the study statistician. Randomization will be 1:1 sildenafil:placebo, and will be in blocks of 2. Investigators associated with this study will not have access to the randomization schedule. The principal investigator, study team, and study subjects will be blinded in this study. To monitor the drug administration, a daily diary will be filled out by the participant. The tolerability of sildenafil in boxers will also be assessed.

A total of 130 boxers will be screened and only 100 boxers will be enrolled in this study to complete the study aims. The study participants will not be responsible for any research related costs, which include travel and parking when visiting UTSWMC for the collection of blood/saliva, neuropsychological testing, and MR imaging. The participants will be compensated for their time.

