## 4.2 STUDY ENDPOINTS

## 4.2.1 PRIMARY ENDPOINT:

To determine if sildenafil administration improves CBF/CVR, reduces symptoms, and improves cognitive performance in concussed boxers/MMA fighters. Hypothesis: Both single and multiple sildenafil therapy improves CBF/CVR, symptoms, and cognition in concussed boxers. Also, long-term administration of daily doses of sildenafil to concussed boxers/MMA fighters is well tolerated. Following injury, we will enroll 100, active boxers/MMA fighters and 80, controls into a double-blind, placebo-controlled study. At a 1:1 ratio, the subjects will receive a single treatment of either placebo or sildenafil. The purpose of this study is to determine if sildenafil treatment improves CBF/CVR, reduces symptoms, and improves cognitive outcomes. In this study we will treat the injured athletes once (within 2 hours of injury) or daily (for 14 days) to determine if sildenafil improves outcomes. Previous clinical studies conducted by our research group, we found that sildenafil treatment (60mg) is tolerable within the TBI population. The athletes will maintain a daily diary of symptoms. At day 1-3 and 30 after injury, the CBF/CVR MR imaging procedures, the Rivermead Post Concussion Symptom Questionnaire, and neuropsychological assessments (NIH Common Data Elements) will be conducted to study the effect of sildenafil therapy. Blood (8cc) and saliva will also be collected to measure brain biomarkers of injury. Tolerability (blood testing and symptom reporting) assessments will be conducted throughout the study to ensure that the symptomatic boxers tolerate multiple, daily doses of sildenafil.

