# 5.3 STRATEGIES FOR RECRUITMENT AND RETENTION

Within the North Texas area there are approximately 130 boxing training centers. Over the last 6 years we have built relationships with trainers at these facilities and about 125 boxers have previously been enrolled in both observational and interventional studies conducted by the [name] laboratory. We have been successful with enrolling athletes (boxers, MMA fighters, etc.) and completing the clinical studies with a very low dropout rate (10%). Thus, we believe that will meet study recruitment and experience very little dropouts.Our target sample size is 100 athletes. We will also recruit 80 healthy controls.

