#### Power analysis and sample size justification

We conducted a power analysis based on the primary endpoints of change in CVR and CBF and correlation of CBF/CVR and symptoms/cognition. Based on the preliminary results, we assume the average changes in CVR between treatment and placebo has an effect size of 0.86. With 50 concussed boxers in each arm, assuming that the correlation between the outcome measures at Day 1-3 and 30 is 0.2, we will achieve 80% power to detect difference in CVR changes comparing sildenafil and placebo effects. If the correlation is 0.5 among outcome measures at all time-points, then with 80% power we only need 34 concussed boxers in each arm. Table 1 demonstrates the needed sample size under a range of effect sizes and within-subject correlations. To understand the correlation between the CVR and post-concussive symptoms among the 50 enrolled boxers (for each group) assessed at three time points, we will have 82.9% power to detect a correlation of 0.4 based on the preliminary results in Table 1 with 95% confidence level.

	Correlation between 3, time-points (rho)							
	0	0.2	0.3	0.5	0.6	0.7	0.8	
Corresponding SD	1.414	1.265	1.183	1	0.894	0.775	0.632	
Effect size	Sample size needed							
0.7	46	38	33	25	21	16	12	
0.86	32	26	23	18	15	12	9	
1	24	20	18	14	12	10	8	
1.2	18	15	14	11	9	8	6	

Table 1: Sample size for each treatment and placebo group under a range of effect sizes and within-subject correlations to achieve 80% power.

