#### Drug Treatment and Randomization:

We will enroll 100 concussed boxers/MMA fighters using a double-blind, placebocontrolled design. The athletes will be randomized at a 1:1 ratio to either placebo or sildenafil for single or multiple doses (once-a-day for 14 days).

A randomization schedule will be prepared by the study statistician. Investigators associated with this study will not have access to the schedule. The PI, study team, and participants will be blinded.

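### The plan enrols 100 athletes in most places and 110-120 in another, the 110-120 range is inflated by the wrong formula, and the power statement makes no allowance for the expected 10-20% dropout

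*Combined protocol and SAP*

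**What the plan says.** Two enrolment figures stand side by side in the combined protocol and SAP.

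- **100.** Section 4.1: "A total of 130 boxers will be screened and only 100 boxers will be enrolled in this study to complete the study aims". Section 4.2.1: "we will enroll 100, active boxers/MMA fighters and 80, controls into a double-blind, placebo-controlled study". Section 10.2.1, drug treatment and randomization: "We will enroll 100 concussed boxers/MMA fighters". Section 5.3 words it as a target: "Our target sample size is 100 athletes". The protocol summary (Population), the procedures table in 7.1.1 and the preliminary analyses in 10.1 also use 100. Section 4.1 splits it into two dosing groups of about 50.
- **110-120.** Section 10.2.1, recruitment and consent: "We expect a dropout rate of 10-20% and will enroll a total of 110-120 boxers to complete the proposed studies".

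On dropout, 5.3 reports 10% in the group's past studies, and 10.2.1 expects 10-20% here.

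The power analysis in 10.1 begins "With 50 concussed boxers in each arm, assuming that the correlation between the outcome measures at Day 1-3 and 30 is 0.2" and claims 80% power for the CVR change with an effect size of 0.86. It then claims 82.9% power for a correlation of 0.4 among 50 boxers per group, whom it describes as enrolled. It does not mention dropout.

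**The concern.** The figures of 100 and 110-120 appear in consecutive paragraphs of 10.2.1, and both 4.1 and 10.2.1 tie their figure to completing the study. A reader cannot tell which one governs the randomisation schedule, the drug order and the number put to the IRB.

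The 110-120 range also looks like dropout added as a percentage on top of the target, which does not return the target once the losses occur. And if 100 is the number randomised, the power statement describes more analysable athletes than the plan itself expects to have at Day 30.

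**Working it through.** **Inputs.** Enrolment of 100 or 110-120 and dropout of 10-20% (sections above). From the power analysis: 50 per arm, effect 0.86, within-subject correlation (rho) 0.2, SD of change 1.265 (its Table 1), correlation 0.4, 95% confidence. I take that as two-sided alpha 0.05, since sidedness is not stated. Fifty per arm assumes the two dosing groups are pooled, because 4.1 puts about 50 athletes in each.

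**1. Where 110-120 comes from.** With d the dropout rate, N × (1 + d) gives 100 × 1.10 = 110 and 100 × 1.20 = 120. The plan's range is reproduced exactly.

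**2. What 100 completers need.** N / (1 − d):
- 10%: 100 / 0.90 = 111.1, so 112 (50 / 0.90 = 55.6, so 56 per arm).
- 20%: 100 / 0.80 = 125 (50 / 0.80 = 62.5, so 63 per arm, 126 with equal arms).

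**3. Completers under each figure.**

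| Enrolled | 10% dropout | 15% | 20% |
|---|---|---|---|
| 100 | 90 | 85 | 80 |
| 110 | 99 | 93.5 | 88 |
| 120 | 108 | 102 | 96 |

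With the ends matched, 110 at 10% leaves 99 and 120 at 20% leaves 96. Enrolling 120 keeps at least 100 as long as dropout does not exceed 1 − 100/120 = 16.7%.

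**4. Correlation power.** Fisher z: power = Φ(√(n − 3) × atanh(0.4) − 1.960), with atanh(0.4) = 0.4236.
- n = 50: Φ(2.904 − 1.960) = 82.8%, against the plan's 82.9%. The plan's figure is reproduced with no dropout.
- n = 45 (50 × 0.90): Φ(2.746 − 1.960) = 78.4%.
- n = 40 (50 × 0.80): Φ(2.577 − 1.960) = 73.1%.

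**5. Power for CVR change, arms pooled.** SD = √(2(1 − 0.2)) = 1.265, so the standardised difference is 0.86 / 1.265 = 0.68. Two-sample t-test, noncentrality 0.68 × √(n/2):
- 50 per arm: 92.0%.
- 45 per arm: 89.1%.
- 40 per arm: 85.2%.

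On these inputs 80% power needs 35 per arm, so the plan's 80% at 50 per arm is not reproduced. That is a separate problem with the power section. Here the calculation shows only how much power dropout removes.

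**The case against.** **The two figures may count different stages.** Section 10.2.1 calls boxers enrolled after the pre-fight consent and before the post-fight re-screen, so 110-120 might count consented boxers and 100 those randomised. This is possible, but the text does not say it. The 110-120 sentence is tied to dropout rather than to failing the re-screen, and 4.1 already covers screening with its 130. What stands is that *enrolled* has no fixed meaning in this protocol, so the correction must begin by defining it.

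**The plan never says it needs 100 completers.** This is correct: the power section calls its 50 enrolled. Section 10.1 also specifies intention-to-treat on all available data, with sensitivity analyses for missing values. An athlete lost after Day 1-3 still contributes to the analysis at that visit, so the reduced numbers apply to Day 30 and to changes that use Day 30. Calling the 50 enrolled does not help the power statement, however: the quoted 82.9% needs 50 observed pairs.

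**The inflation error is small.** It is one athlete at 10% and four at 20%, so it matters only near the upper end.

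**Stronger readings that the documents do not support.**
- A reader might infer that neither enrolment figure can deliver 100 completers. Enrolling 120 delivers 102-108 at 10-15% dropout, and 110 at 10% misses by one.
- A reader might infer that dropout leaves the CVR comparison underpowered, because the plan claims just 80% at 50 per arm. On the stated effect and correlation at two-sided 0.05, power stays at 85% or more. Some stricter alpha could give 80% at 50 and less after losses, but the plan states none.
- A reader might also attribute low power within a single dosing regimen to dropout. That comes mainly from dividing each group of about 50 into two arms and is a different question.

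**Conclusion.** The concern holds in limited form.

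- **Conflict in the figures.** 100 against 110-120, with the stage undefined. This rests on the text alone.
- **Inflation formula.** The range should be 112-125 (126 with equal arms) if 100 completers are intended. The shortfall is material only near 20% dropout.
- **No dropout allowance in the power statement.** If 100 are randomised, 80-90 are expected to complete. The stated correlation power then falls below 80%, to about 78% at 45 and 73% at 40. Pooled CVR power loses 3 to 7 percentage points from 92% and remains above 80%.

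The power figures assume two-sided alpha 0.05, dropout of 10-20% spread evenly over arms and groups, dropouts contributing no Day 30 data, and, for CVR, pooling of the dosing groups. The design is not undermined, but the sample size is a figure the trial relies on and should be stated once and correctly.

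**What to change.** 1. Choose one enrolment number and say whether it counts consented, randomised or completing athletes. Use it, with that label, everywhere: protocol summary, 4.1 (including the group sizes), 4.2.1, 5.3, the table in 7.1.1, 10.1 (preliminary analyses and power analysis) and both paragraphs of 10.2.1.
2. If 100 are randomised, delete 110-120 as an enrolment figure, or relabel it if it means consented boxers. Restate power for 80-90 completers: for the correlation, about 78% at 45 and 73% at 40 per group. State alpha and sidedness. Give the CVR figure at 40-45 per arm once the base calculation has been reconciled.
3. If 100 completers are intended, replace 110-120 with 112-126. The 130 to be screened would then need revising: at the plan's own ratio of 130 screened per 100 enrolled, 112-126 implies about 146-164 (112 × 1.3 = 145.6; 126 × 1.3 = 163.8).

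Option 2 is enough. It changes wording only and needs no extra participants. Option 3 adds 12 to 26 randomised athletes relative to 100, plus the screening to find them.
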